4.2.5 SUBJECT TRAINING

Subjects will be issued transmitters as appropriate and trained in their use along with a hand-held device which will be used for entering calibration information.

The subject will be given instructions on how to contact study staff for 24 hours per day to report any study- related problems. The subject will be instructed to contact the study staff for prolonged hyperglycemia, severe hypoglycemia, or if he/she experiences nausea, vomiting, or abdominal pain within 48 hours after discharge. The subject will be instructed to contact the study staff for any problems related to the sensor sites, including fever, pain, redness, itching, discharge, warmth or swelling at the sensor insertion sites. If infection is experienced, standard medical practice and administration of antibiotics as required should be followed until resolution. Subjects will be further instructed to advise the investigator if new medications have been prescribed or started, or if any hospitalizations or significant medical changes have occurred.

The subject will be instructed on the proper use and quality control of the Subject SMBG Meter including the number and timing of fingersticks expected during each day (approximately 7 times per day (before meals, approximately 2 hours after meals, and at bedtime)). Subjects will be requested to enter all SMBG readings into the Eversense® app as glucose events. Subjects will be monitored for compliance to a minimum of 4 SMBG readings per day including at least 1 pre-prandial and 1 before bedtime, and will be contacted by the study site if they are found to be out of compliance. Subjects will be requested to enter all insulin injections/boluses into the Eversense app to aid in evaluation of subject compliance with adjunctive use of the CGM system.

The subject will be instructed on the proper use of the Transmitter and Mobile Medical Application (refer to the Eversense® 180 CGM User Guides). The transmitter(s) will be worn over the sensor at all times (except while charging) starting approximately 24 hours post insertion. Subjects will be prompted to calibrate the sensor using fingerstick measurements using the Subject SMBG meter.

4.2.6 DISCHARGE

Discharge will occur upon completion of confirmation of system operation and subject training. The site will document any adverse events that may have occurred during the visit.

4.2.7 ESTIMATED VISIT DURATION

The total duration of the inpatient visit is approximately 2-3 hours

4.2.8 SUBJECTS ASSIGNED TO Day 1 Early Shift Group

Subjects in Day 1 Early Shift Group will leave their transmitters at the clinical site and will return the following day for visit 3A sensor accuracy visit. They will place the transmitters and perform their first calibrations at the clinical site as prompted by the Eversense® 180 CGM System.

4.2.9 SUBJECTS ASSIGNED TO Day 1 Middle and Late Shift Groups

Subjects in Day 1 Middle and Late Shift Groups will be instructed to start wearing the transmitters approximately 24 hours after the sensor was inserted. Subjects will then be prompted by the Eversense® 180 CGM System to enter their first calibration, and the Eversense® 180 system will enter the initialization phase. The clinical site should communicate with the subject during this time to make sure the subject was successful with entering initialization.

4.2.10 SUBJECTS WITH TWO SENSORS INSERTED

Subjects with two sensors inserted will be issued two transmitters to be worn over the sensors. Transmitters will be designated as primary (left arm) and secondary (right arm) and will have distinguishing visual marks to ensure matching to the correct limb. Each transmitter is linked to a specific sensor as described in the Eversense® 180 CGM system User Guide. Subjects will be issued a hand-held display which will be used for entering calibration information into the primary transmitter only. The secondary transmitter worn on the opposite arm will have the ability to collect and log data only and will not calculate and store glucose. The handheld device, when paired to the secondary transmitter, will only display battery level and the placement guide used for wearing the transmitter as described in the Eversense® 180 CGM system User Guide.

The secondary transmitter will use the SMBG calibration points collected and entered into the primary system (using the same time stamp information) for calculation of glucose results in the analysis data set.

This subset of subjects will be used to explore the following endpoints: PARD, and dominant vs non-dominant arm effects. Analysis of data from subjects with two sensors inserted is further described in Section 11. Additionally, this subset of subjects will continue participation for 365 days of sensor wear. At Day 180, the primary sensor will be removed and a new sensor will be inserted. The secondary sensor will remain in situ for observation of sensor life for up to 365 days.

4.3 SENSOR ACCURACY VISITS

Day 1 (Day 1 Early Shift Group only) – Visits 3A

Approximate visit duration - 11 hours

Approximate sampling duration – 8 hours

Approximate visit timeline:

Approximate time*	Activity**	Time relative to first IV sample
~06:00	Admission	T=0 -2:00
~07:15-07:45	Free range glucose control	T=0 -0:45 - -0:15
~08:00	First IV blood sample drawn	T=0 0:00
~08:00 – 13:00	For qualifying subjects, hypoglycemia challenge to achieve hypoglycemia target <70 mg/dL for 1 hour 
Sampling every 5 min when glucose ≤70 mg/dLChallenge may be stopped once 13 YSI values ≤70 mg/dL are collectedSubjects fed at end of challengeNote: Subjects should not be held <55 mg/dL for more than 20 minutes	T=0 0:00 – +5:00

Approximate time*	Activity**	Time relative to first IV sample
~08:00 – 13:00	Alternatively, for qualifying subjects, hyperglycemia challenge to achieve hyperglycemia target >300 mg/dL for 75 minutes 
 Sampling every 5 min when glucose ≥300 mg/dL Challenge may be stopped once 16 YSI values ≥300 mg/dL are collected 	T=0 0:00 – +5:00
~08:00 – 13:00	For those subjects not following a basal/bolus routine on MDI or CSII, glucose control will be free range	T=0 0:00 – +5:00
~09:00	Fingerstick blood glucose	T=0 +1:00
~10:00	Fingerstick blood glucose	T=0 +2:00
~11:00	Fingerstick blood glucose	T=0 +3:00
~12:00	Fingerstick blood glucose	T=0 +4:00
~13:00	Fingerstick blood glucose	T=0 +5:00
~13:00-16:00	Recovery Period with meal/bolus and glucose stabilization	T=0 +5:00 - +8:00
~14:00	Fingerstick blood glucose	T=0 +6:00
~15:00	Fingerstick blood glucose	T=0 +7:00
~16:00	Fingerstick blood glucose	T=0 +8:00
~ 15:00 – 16:00	Discharge preparation period	
~16:00	Last IV blood sample draw	T=0 +8:00
~16:30	Discharge	T=0 +8:30

*Times may change based on time sensors are inserted.

** CGM calibration will be performed as prompted by the Eversense® 180 CGM System throughout the visit.

Other 8-Hour Sampling Sensor Accuracy Visits – Visits 3B (Day 1 Middle Shift Group), 3C

(Day 1 Late shift Group) and Visits 4-10 (all subjects)

Approximate visit duration - 10 hours

Approximate sampling duration – 8 hours

Approximate time*	Activity**	Time relative to first IV sample
~07:30	Admission	T=0 -:30
~07:30-07:45	Free range glucose control	T=0 -0:45 - -0:15
~08:00	First IV blood sample drawn.	T=0 0:00

Approximate time*	Activity**	Time relative to first IV sample
~08:00 – 13:00	For qualifying subjects, hypoglycemia challenge to achieve hypoglycemia target <70 mg/dL for 1 hour 
 Sampling every 5 min when glucose ≤70 mg/dL Challenge may be stopped once 13 YSI values ≤70 mg/dL are collected Subjects fed at end of challenge Note: Subjects should not be held <55 mg/dL for more than 20 minutes 	T=0 0:00 – +5:00
~08:00 – 13:00	Alternatively, for qualifying subjects, hyperglycemia challenge to achieve hyperglycemia target >300 mg/dL for 75 minutes 
 Sampling every 5 min when glucose ≥300 mg/dL Challenge may be stopped once 16 YSI values ≥300 mg/dL are collected 	T=0 0:00 – +5:00
~08:00 – 13:00	For those subjects not following a basal/bolus routine on MDI or CSII, glucose control will be free range	T=0 0:00 – +5:00
~09:00	Fingerstick blood glucose	T=0 +1:00
~10:00	Fingerstick blood glucose	T=0 +2:00
~11:00	Fingerstick blood glucose	T=0 +3:00
~12:00	Fingerstick blood glucose	T=0 +4:00
~13:00	Fingerstick blood glucose	T=0 +5:00
~13:00-16:00	Recovery Period with meal/bolus and glucose stabilization	T=0 +5:00 - +8:00
~14:00	Fingerstick blood glucose	T=0 +6:00
~15:00	Fingerstick blood glucose	T=0 +7:00
~16:00	Fingerstick blood glucose	T=0 +8:00
~ 15:00 – 16:00	Discharge preparation period	
~16:00	Last IV blood sample draw	T=0 +8:00
~16:30	Discharge	T=0 +8:30

*Times may change based on time sensors are inserted.

** CGM calibration will be performed as prompted by the Eversense® 180 CGM System throughout the visit.

10-Hour Sampling Sensor Accuracy Visit –Visit 11 (all subjects)

Approximate visit duration - 12 hours

Approximate sampling duration – 10 hours

Approximate time	Activity**	Time relative to first IV sample
~07:30	Admission	T=0 -:30
~07:30-07:45	Free range glucose control	T=0 -0:45 - -0:15
~08:00	First IV blood sample drawn	T=0 0:00
~08:00 – 13:00	For qualifying subjects, hypoglycemia challenge to achieve hypoglycemia target <70 mg/dL for 1 hour 
 Sampling every 5 min when glucose ≤70 mg/dL Challenge may be stopped once 13 YSI values ≤70 mg/dL are collected Subjects fed at end of challenge Note: Subjects should not be held <55 mg/dL for more than 20 minutes 	T=0 0:00 – +5:00
~08:00 – 13:00	Alternatively, for qualifying subjects, hyperglycemia challenge to achieve hyperglycemia target >300 mg/dL for 75 minutes 
 Sampling every 5 min when glucose ≥300 mg/dL Challenge may be stopped once 16 YSI values ≥300 mg/dL are collected 	T=0 0:00 – +5:00
~08:00 – 13:00	For those subjects not following a basal/bolus routine on MDI or CSII, glucose control will be free range	T=0 0:00 – +5:00
~09:00	Fingerstick blood glucose	T=0 +1:00
~10:00	Fingerstick blood glucose	T=0 +2:00
~11:00	Fingerstick blood glucose	T=0 +3:00
~12:00	Fingerstick blood glucose	T=0 +4:00
~13:00	Fingerstick blood glucose	T=0 +5:00
~13:00-18:00	Recovery Period with meal/bolus and glucose stabilization	T=0 +5:00 - +8:00
~14:00	Fingerstick blood glucose	T=0 +6:00
~15:00	Fingerstick blood glucose	T=0 +7:00
~16:00	Fingerstick blood glucose	T=0 +8:00
~17:00	Fingerstick blood glucose	T=0 +9:00

Approximate time	Activity**	Time relative to first IV sample
~18:00	Fingerstick blood glucose	T=0 +10:00
~ 17:00 – 18:00	Discharge preparation period	
~18:00	Last IV blood sample draw	T=0 +10:00
~18:30	Discharge	T=0 +10:30

** CGM calibration will be performed as prompted by the Eversense® 180 CGM System throughout the visit.

4.3.1 THE FOLLOWING PROCEDURES/INSTRUCTIONS WILL BE FOLLOWED FOR ALL ACCURACY VISITS

4.3.1.1 PRE-VISIT PHONE CALL (DAY 7-180 VISITS)

Approximately 12 hours prior to the Accuracy Visit, site personnel will contact the subject to ensure the subject is in compliance with study device wear prior to the scheduled start of glucose sampling. Subjects may be instructed to calibrate at a specific number of hours before the scheduled visit start in order to assess accuracy over the entire calibration window. Subjects may also be given appropriate instructions regarding pre-visit medications and meals.

4.3.1.2 SUBJECT INSTRUCTIONS PRIOR TO ADMISSION

Prior to admission, subjects should take morning medications as usual as follows:

- If challenge subjects need to eat or take insulin for safety reasons, they should inform study staff of this information on arrival to the clinic.
- Subjects should consume the food they would normally consume to treat or prevent hypoglycemia at the blood glucose level they feel is appropriate.

A clinician trained in the treatment of diabetes should also discuss and make recommendations about each subject's insulin regimen for the remainder of the day to prevent post-visit rebound hypoglycemia which can occur 12 hours later.

4.3.1.3 DEVICE SET UP

4.3.1.3.1 DEVICE CALIBRATION

Prior to subject blood sampling, the CRC study equipment (YSI glucose analyzer, ketone meter and study-supplied Subject SMBG Meter) will be checked for proper function and the appropriate quality controls will be run per the manufacturer's guidelines as appropriate.

4.3.1.3.2 TIME SYNC

At each study visit the date and time on all study devices (i.e. study clocks, laptop(s), Subject SMBG Meter, Reference instrument and Eversense® 180 Continuous Glucose Monitoring System) will be synchronized at the start of the visit to the Official US Time using www.time.gov or to an equivalent atomic clock.

The study devices do not all automatically adjust for daylight savings time. Subjects should not adjust the study device times on their own – they should wait until someone at the clinic can adjust the time so any offsets can be documented in order to reconcile the data.

4.3.2 MEDICATIONS AND MEDICAL SUPPLIES

All medications and medical supplies required for the Clinical Research Center (CRC) hypoglycemia and hyperglycemia treatment protocols will be readily available at the time of subject treatment including a code cart. The subject will be rescheduled if he/she did not bring his/her required medications or appropriate medications are not available at the clinic.

4.3.3 SUBJECT ADMISSION

The subject will arrive at the clinic and the following tests will be performed to confirm eligibility for participation in the visits:

- Hematocrit will be assessed using local lab or Point of Care testing device. Subject must be within reference range to participate in accuracy visit.
- Female subjects of childbearing capacity will perform a urine pregnancy test. If positive, the subject will discontinue study participation. Subject withdrawal will be documented.
- Study subjects using tetracyclines within 4 days of visit start will be asked to reschedule the visit.
- Study subjects using sorbitol/mannitol within 12 hours of visit start will be asked to reschedule the visit.
- The study team will confirm the absence of a febrile or vomiting illness within 24 hours of the admission.
- The study team will confirm that the subject brought his/her personal insulin and insulin pump or injection supplies (as applicable) and regular medications. The subject will continue to use his/her diabetes treatment regimen throughout the admission. The subject will be rescheduled if he/she did not bring his/her regular medications or appropriate medications are not available at the clinic.

- Clinical staff to confirm that the subject is wearing the transmitter and that the transmitter and hand-held device are in communication and functioning.
- The subject will be rescheduled if he/she did not bring his/her Transmitter and cannot make them available during the visit.

If all admission readiness criteria are not met, the subject will be rescheduled. If all of the admission readiness conditions are met, the subject will be admitted to the Clinical Research Unit.

4.3.4 ADVERSE EVENTS

Upon admission subject will be asked about any adverse events or changes in medication since the last study visit. If subjects experienced DKA or Severe hypoglycemia during the past 30 days, they will be excluded from participating in the glucose challenge, but may continue with the accuracy visit under observation only. The sensor insertion site will be examined. Adverse events including those associated with the insertion site will be documented on the appropriate eCRF.

4.3.5 KETONE TESTING

Ketone (β -hydroxybutyrate (β -HOB)) measurements will be made using a study supplied FDA-approved self-monitoring ketone meter and strips as described in 5.2.3. Subject blood ketones should be evaluated from capillary or venous blood using the ketone meter while in the clinic for sensor insertion and accuracy visits at the following times:

- On arrival and at discharge from the clinic
- Glucose ≥ 300 mg/dL (measure approximately within 20 minutes of the first glucose reading > 300 mg/dL and repeat approximately every 60 minutes until < 300 mg/dL)
- Ketones ≥ 0.6 mmol/L (repeat approximately every 60 minutes until < 0.6 mmol/L)
- Subject has nausea, vomiting or abdominal pain regardless of glucose level.

Treatment guidelines for ketones can be found in section 7.5.3.

4.3.6 SMBG TESTING

During in-clinic days, subjects should continue testing blood glucose using the study-supplied Subject SMBG Meter following the schedule for each visit (hourly). For home use periods, it is requested that subjects test approximately 7 times per day (before meals, 2 hours after meals, and at bedtime). Subjects will be requested to enter all SMBG readings into the Eversense® app as glucose events. Subjects will be monitored for compliance to a minimum of 4 SMBG readings per day including at least one pre-prandial and one bedtime reading, and will be contacted by the study site if they are found to be out of

compliance. Subjects will be requested to enter all insulin injections/boluses into the Eversense app to aid in evaluation of subject compliance with adjunctive use of the CGM system.

All fingersticks for capillary blood glucose testing will be preceded by hand washing (with soap, warm water and a dry towel), or by using an alcohol swab and allowing the area to air dry.

4.3.7 SYSTEM CALIBRATION

The Eversense® 180 Continuous Glucose Monitoring (CGM) System (primary sensor) will be calibrated and maintained per Eversense® 180 CGM User Guide. After the initialization period (approx. 30 hours after sensor insertion), the system enters the Daily Calibration phase. For this study, subjects should follow the recommendations below:

4.3.7.1 IN CLINIC

During the in-clinic sessions, subjects will calibrate as prompted by the Eversense® 180 CGM System.

4.3.7.2 AT HOME

During periods of home use, it is required to calibrate the Eversense® 180 CGM System using SMBG values from the study-supplied meter, the Contour Next One blood glucose meter. Calibration is best done when glucose is neither rapidly rising nor falling. The Eversense® 180 CGM System will prompt the user when it is time to calibrate.

4.3.8 USE OF STUDY DEVICES FOR DIABETES TREATMENT

For the duration of the study, all diabetes care decisions will be based on reference blood glucose values or SMBG as appropriate, rather than Eversense® 180 CGM System results.

4.3.9 IV/BLOOD DRAW GUIDELINES

4.3.9.1 IV PLACEMENT/SETUP

IVs for blood sampling may be placed in the arm or hand. IV Access will be maintained during the sampling portion of the study for blood sampling and for the treatment of severe hypoglycemia or hyperglycemia during the study. If an IV fails, a reasonable effort should be made to replace it.

It is advised that sites use a heating pad in order to help keep IV sampling sites patent and improve blood flow.

4.3.9.2 TIMING OF BLOOD SAMPLING

Blood will be sampled approximately every 5 to 15 minutes, dependent on the value of the previous sample according to the following ranges:

- BG \geq 300 mg/dL: every 5 minutes (+/- 2 minutes) *
- BG >70 mg/dL and < 300 mg/dL: every 15 minutes (+/- 2 minutes)
- BG \leq 70 mg/dL: every 5 minutes (+/- 2 minutes)

*When > 400 mg/dL, sampling may be reduced to every 15 minutes

Blood sampling can also be reduced to every 15 minutes after the challenge is met. Additional samples may be drawn for YSI glucose analysis as needed for patient safety or to recheck a suspected erroneous value (e.g. dilute sample).

In the event of loss of IV access or loss of functional YSI and need for continued subject monitoring, glucose measurements will be made on capillary whole blood using the Subject SMBG meter as needed.

Samples missed due to loss of IV access or other interruptions will not be considered protocol deviations.

4.3.9.3 SAMPLE VOLUME

Approximately 0.5 ml IV blood samples will be collected (after 1.5 ml waste is cleared from sampling apparatus) in sample containers with an appropriate anticoagulant additive (BD Microtainer K2E tubes (REF 365955) or Sarstedt Monovette with K2E (REF 06.1664.001) or similar) for analysis.

4.3.9.4 CENTRIFUGE

Centrifuge sample to sufficiently separate the plasma, approximately 30 seconds in StatSpin Express 2 (or similar) centrifuge (8500 rpm).

Samples centrifugation should begin as soon as possible after the blood draw (within a maximum of 3 minutes). Samples should be discarded if not run within this time frame.

4.3.10 GLUCOSE CHALLENGES

4.3.10.1 SUBJECT ELIGIBILITY

Subjects not on insulin therapy will not be expected to undergo hypoglycemic challenges. Eligible subjects will be required to participate in glucose challenges. Subjects unable to participate in glucose challenges will participate in the accuracy sessions using free range glucose control.

4.3.10.2 GUIDELINES FOR DETERMINING WHICH CHALLENGE TO CHOOSE (ALL VISITS)

Subject BG levels and direction of those levels determined using the first three SMBG/YSI readings will inform whether the subject will participate in the hypoglycemia or hyperglycemia challenge on that study day, according to the following table as a guideline:

Glucose level	Challenge*
<180 mg/dL	Hypoglycemia challenge
≥180 mg/dL	Hyperglycemia challenge

*Investigator discretion and patient safety will also be considered in determining appropriate challenge. Additional SMBG can be done to determine the appropriate challenge.

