11.1.2 DATA POOLING

Subjects will be selected consecutively (i.e., selecting every subject in the order they present at the site) among those who meet the inclusion/exclusion criteria. All subjects will receive sensors and transmitters. The primary effectiveness measure (MARD) will be analyzed with data pooling across sites. Site effects will be examined, but only descriptively.

Analyses will be performed based on aggregating all patients in the study, and again separately for each randomized groups. The analysis by randomized groups will be only performed descriptively and there will be no formal statistical comparisons. Transmitters will be designated as primary (left arm) and secondary (right arm).

Analyses will be performed for subgroup of interest (based on type of diabetes (type I vs. type 2), age (\geq 65 years of age vs. $<$ 65), and baseline HbA1c (\geq 8% vs. $<$ 8%).

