6.9 Additional Analyses

Descriptive analysis will be carried out on data from all participants, and separately for each of the following groups. No hypothesis testing on the difference between groups will be carried out.

- Type 1 versus Type 2 diabetes mellitus.
- Age (18-20, 21-44, 45-65, and over 65 years)
- Baseline HbA1c level below 8% versus 8% or over
- Glucose range strata (e.g. <40, 40-60, 61-80, 81-180, 181-300, 301-350, 351-400, > 400 mg/dL) to include all samples, i.e. more frequent than 15-minute sampling

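### Subgroup MARDs by HbA1c and diabetes type are not adjusted for glucose range, although the challenge rules can give the subgroups different glucose mixes

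*Protocol*

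**What the plan says.** **Choice of challenge.** Protocol 4.3.10.2: "Subject BG levels and direction of those levels determined using the first three SMBG/YSI readings will inform whether the subject will participate" in one challenge or the other. The guideline table sends readings below 180 mg/dL to hypoglycemia and readings of 180 mg/dL or more to hyperglycemia. A footnote adds: "Investigator discretion and patient safety will also be considered in determining appropriate challenge".

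**Who is challenged.** The visit timelines in protocol 4.3 state: "For those subjects not following a basal/bolus routine on MDI or CSII, glucose control will be free range". Protocol 4.3.10.1 has a narrower exclusion: "Subjects not on insulin therapy will not be expected to undergo hypoglycemic challenges".

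**What a challenge adds.** For hypoglycemia: "Challenge may be stopped once 13 YSI values ≤70 mg/dL are collected". For hyperglycemia: "Challenge may be stopped once 16 YSI values ≥300 mg/dL are collected". Protocol 4.3.9.2 samples every 5 minutes at or below 70 and at or above 300 mg/dL, and every 15 minutes in between.

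**Subgroup results.** Protocol 11.1.2: "Analyses will be performed for subgroup of interest", naming diabetes type, age and baseline HbA1c. SAP 6.9 lists "Baseline HbA1c level below 8% versus 8% or over" and type 1 versus type 2, with glucose-range strata as a separate item in the same list. MARD is an unweighted mean over pairs (protocol 11.3.2.1; written per participant in SAP 6.6.2).

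**Data sets.** The SAP's primary effectiveness set (6.2) keeps reference values at 15-minute intervals. SAP 6.9 brings in the more frequent samples only for the glucose-range strata. Protocol 11.1.6 uses all data.

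**The concern.** A hypoglycemia session contributes low and middle pairs but no high ones; a hyperglycemia session contributes middle and high pairs but no low ones. HbA1c reflects usual glucose, so subjects at 8% or over may start more visits at or above 180 mg/dL and have hyperglycemia challenges more often. Type 2 subjects who are off insulin, or not on a basal/bolus routine, may have fewer challenges or none. If relative error varies with glucose, a subgroup MARD then partly reflects which sessions the subgroup had.

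Protocol 11.3.2.2 and SAP section 5 set a target of 20 subjects per subgroup so that the subgroups can be characterised. With no tests or models planned, the descriptive figure is the whole result, and nothing later in the analysis corrects it for glucose mix. Readers will take it as sensor accuracy in those patients.

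**Working it through.** **1. Pairs per session, checked against protocol 11.1.4.** An 8-hour visit on a 15-minute grid has 480/15 + 1 = 33 samples. One hour covers 5 grid points and 75 minutes covers 6.
- Hypoglycemia: 13 low + (33 − 5) = 28 middle, 41 in all.
- Hyperglycemia: (33 − 6) = 27 middle + 16 high, 43 in all.
- Half of each: 6.5 / 27.5 / 8 (low/middle/high). For the 10-hour day-180 visit: 6.5 / 35.5 / 8.

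The 8-hour visits in the table sum to 1,225 subject-visits, and day 180 adds 112 to 120. At 112: low 1,225 × 6.5 + 112 × 6.5 = 8,690.5; middle 1,225 × 27.5 + 112 × 35.5 = 37,663.5; high 1,225 × 8 + 112 × 8 = 10,696; total 57,050. At 120 the total is 57,450. These match the protocol's figures apart from rounding.

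**2. Mix by session type.**

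| Session | All samples | 15-minute set |
|---|---|---|
| Hypoglycemia | 13 / 28 / 0 | 5 / 28 / 0 |
| Hyperglycemia | 0 / 27 / 16 | 0 / 27 / 6 |
| Free range (assumed all middle) | 0 / 33 / 0 | 0 / 33 / 0 |

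**3. Formula.** Subgroup MARD = Σ(pairs in range × range MARD) / Σ(pairs in range), with the same range MARDs in every subgroup. The range MARDs and session shares below are assumptions.

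**4. HbA1c, central case.** Range MARDs 14/9/7%; hypoglycemia share 70% below 8% and 30% at 8% or over.
- 15-minute set, below 8%: (3.5 × 14 + 27.7 × 9 + 1.8 × 7)/33 = 310.9/33 = 9.42%.
- 15-minute set, 8% or over: (1.5 × 14 + 27.3 × 9 + 4.2 × 7)/33 = 296.1/33 = 8.97%. Gap 0.45 points.
- All samples: 410.3/41.6 = 9.86% versus 378.7/42.4 = 8.93%. Gap 0.93 points.

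**5. HbA1c, range of assumptions.**

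| Range MARDs; hypoglycemia shares | 15-minute gap | All-sample gap |
|---|---|---|
| 9/9/9; any split | 0.00 | 0.00 |
| 12/9/7.5; 60 v 40% | 0.15 | 0.30 |
| 14/9/7; 70 v 30% | 0.45 | 0.93 |
| 16/9/7; 80 v 20% | 0.85 | 1.78 |

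Masking works the same way. In the central 15-minute case, a sensor truly worse by 0.45 points at every glucose level in the 8%-or-over group would show 9.42% in both groups.

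**6. Diabetes type, 15-minute set, 14/9/7.** Type 1 challenged half and half: (2.5 × 14 + 27.5 × 9 + 3 × 7)/33 = 303.5/33 = 9.20%.
- Type 2 fully free range (extreme under the 4.3 timelines): 9.00%. Gap 0.20.
- Type 2 with hyperglycemia challenges only (extreme under 4.3.10.1): (27 × 9 + 6 × 7)/33 = 285/33 = 8.64%. Gap 0.56.
- The effects can cancel. With 10.2/9/8, type 1 is (25.5 + 247.5 + 24)/33 = 9.00%, equal to fully free-range type 2.

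**7. Check of the fix.** Weighting both HbA1c groups of step 4 to a common 2.5/27.5/3 mix gives 303.5/33 = 9.20% in each; the gap is 0.00. The same holds in every equal-accuracy scenario, because the weights no longer depend on the subgroup.

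**The case against.** - **The crossing may be intended.** SAP 6.9 says descriptive analysis is carried out separately for each group, and that analysis includes accuracy by YSI range. A sponsor could fairly read this as range tables within each subgroup. But range is listed as its own grouping, no visible text or sample table crosses it with a subgroup, and not all appendix pages were available. The crossing is therefore possible but not secured, and standardisation is not mentioned.
- **Nothing shows that relative error varies with glucose.** Correct: the documents give no MARD by range. The switch to mg/dL at 80 and below, and the planned range tables, suggest the sponsor expects it to vary, but that is only a hint.
- **The routing is inferred.** This stands. The rule uses same-day glucose, is a guideline, and leaves room for discretion; HbA1c is not mentioned. The planning table assumes challenges split equally. Eligibility turns on insulin regimen, so type 2 subjects on MDI or CSII can be challenged.
- **The 15-minute set weakens the effect.** It roughly halves it, and it is the SAP's primary set. The all-sample figures apply to the population in protocol 11.1.6.
- **Subgroups are descriptive only.** True, and it limits the harm to how the figures are read.

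A reader might infer that the subgroup MARDs must differ, or that they mainly show which challenge each subgroup had. Neither follows. The gap is zero with flat error, and in the central 15-minute case about 83-84% of pairs in both HbA1c groups are middle range.

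**Conclusion.** The point holds as a possible distortion of unknown size. The rules can produce different glucose mixes by HbA1c and diabetes type, and the planned subgroup MARDs do not account for this. They can therefore differ, or conceal a difference, with equal accuracy at each glucose level.

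For HbA1c, 0.15-0.85 points is the range to use for the SAP's primary set, and 0.3-1.8 points for all samples. For diabetes type, with 14/9/7, the two extremes in the 15-minute set are about 0.2 and 0.6 points. All of this rests on assumed range MARDs and session shares. It would be wrong to say that subjects at 8% or over are mostly sent to hyperglycemia challenges, or that type 2 subjects are usually left free range: the documents give no such shares. The overall MARD and the safety results are not touched. This is a worthwhile improvement to descriptive tables, not a flaw in the main result.

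**What to change.** In SAP 6.9 and protocol 11.1.2, for the diabetes-type and HbA1c subgroups:

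1. Report accuracy and agreement within the SAP's YSI strata, collapsed where sparse, keeping the mg/dL convention at YSI 80 mg/dL and below in those rows.
2. Beside the crude MARD, give a percent MARD standardised to the pooled YSI-range distribution of the same analysis set.
3. Show the number of hypoglycemia, hyperglycemia and free-range sessions per subgroup.
4. Withhold the standardised figure where a subgroup has almost no pairs in a range.

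The challenge-eligibility wording in 4.3 and 4.3.10.1 should also be reconciled, since the expected mix depends on which applies.

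The cost is SAP wording and some table rows from data already collected; no visit or procedure changes. The downside is lower precision, and sparse low-range cells, in subgroups near the target of 20.
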